## 5. TRIAL SCHEDULE

The study will commence in 2018, with randomisation of half of the men during the first year. The first screening round will be completed in 2019. A summary of the timeline is shown in Table 1.

Table 1. Planned schedule of the trial conduct

	Trial years 1-2	Years 3-4	Years 5-6	Years 7-8	Years 9-10
All subjects	Recruitment				
All participants	1 st screening				
Men with PSA>3		2 nd screen	3 rd screen	4 th screen	5 th screen
Men with PSA 1.5-3			2 nd screen		3 rd screen
Men with PSA<1.5				2 nd screen	

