## 6. POWER CALCULATIONS & STATISTICAL ANALYSIS PLAN

The main outcome of the trial is prostate cancer mortality. An intention to screen analysis will be performed, with all men in the groups defined by random allocation, regardless of compliance. This is the gold standard for randomised trials, as it gives an unbiased effectiveness estimate, which is realistic for application (though lower and 'diluted' compared with an efficacy estimate based on compliers only). The only post-randomisation exclusions will be based on prostate cancer diagnosis prior to entry, as inevitably some recent cases will be found out only after randomisation. Follow-up starts at randomisation, and ends at death. Dates of death are registered also for men who have emigrated, but in case of a missing cause of death, the event will be censored. Cox regression will be used with prostate cancer death as the outcome. Randomisation is expected to result in balanced distribution of age, with no need for adjustment.

Based on the most recent age-specific population rates (2010-2014) and the age structure of the male population, the expected number of prostate cancer deaths in the control arm is 222 at 10 years, with sufficient statistical power ( $1-\beta=0.8$ ,  $\alpha=0.05$  two-sided) to detect a 33% reduction (hazard ratio,  $HR\leq 0.67$  for the screening arm, cumulative mortality 29 vs. 44 per 10,000 men) in prostate cancer mortality. This is calculated considering the overall mortality from other causes (ranging from 7 per 100,000 at age 55 to 210 per 100,000 at age 75), yielding a total of 475,000 person-years of follow-up. At 15 years of follow-up, the expected number of deaths in the control arm is 451, with a minimal detectable effect size of 26% ( $HR\leq 0.74$ , 67 vs. 90 deaths per 10,000 men, based 912,800 person-years of follow-up).

A secondary analysis of prostate cancer mortality will be performed using the Cuzick method to correct for non-compliance and contamination (Cuzick 1997, Roobol 2009, Kilpeläinen 2015).

Intermediate outcomes include cumulative incidence of advanced (T3-T4 or M1) prostate cancer (number of cases relative to population size, not using incidence density to avoid the lead-time bias due to early

detection by screening), and cumulative incidence of low-risk cancer (Gleason<7) as an indicator of overdiagnosis.

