are performed at five and eight years in accordance with sequential analysis rules (total alpha spending 0.005 of the two interim analyses according O'Brien-Fleming).

The study question satisfies equipoise criteria, i.e. balance of uncertainty (superiority of the evaluated intervention versus standard practice is not established). All procedures applied represent viable clinical options meeting current standards of care. The two screening tests based on a blood sample constitute the only experimental procedure performed solely for research purposes. Hence, the allocation based on randomisation is the only deviation from the normal health care and patient management. Screen-positive men are referred to diagnostic examinations just as any other patients, and undergo the procedures similar to other patients. This means that the results are readily applicable to public health policy. The generalisability is further enhanced by the Zelen-type randomisation, with consent sought only from the men in the intervention arm after randomisation. This ensures ethical conduct of research, as nobody is denied access to proper health care by the randomisation.

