## 8. RISKS

The fundamental idea of the trial is the uncertainty about the effects of prostate cancer screening and the rationale rests on the assumption that the approaches, which have never been evaluated in a randomised trial and never combined into a single protocol, can be successfully integrated into a winning formula. However, a RCT has the advantage that even in a negative result is informative, i.e. proving that the proposed concept does not work, advances our understanding of the issue, here prostate cancer screening. The study is unique, and the closest counterparts either use PSA alone and lack one layer of risk stratification (Göteborg2 study) or have entirely failed to use randomisation (Sthlm3 study) and hence fall short of the scope of the present proposal.

Among the less fundamental issues, we expect a similar participation proportion as in the previous Finnish screening trial (67% at the initial round, and a similar level retained in the subsequent rounds).

The anticipated effect size, i.e. magnitude of mortality reduction achievable may be overstated. In the European screening trial (ERSPC), the relative reduction in prostate cancer has remained at 20% from 9 years to 13 years of follow-up (Schröder 2009, 2014). If the two risk stratification methods used for screening (kallikrein panel and MRI) both have 90% sensitivity for clinically relevant prostate cancer, a realistic effect size might be  $0.9 \times 0.9 \times 0.2 = 0.16$  i.e. 16% reduction. However, the shorter screening interval for men with PSA >3 is likely to compensate this at least partly. For instance, the majority of prostate cancer deaths up to 19 years of follow-up was among men with a baseline PSA >3 in the screening participants in the previous Finnish trial, suggesting that the shorter screening interval in such men is likely to enhance the screening effect.

Prostate cancer mortality has declined in Finland from 60 to 50 per 100,000 in 2002-2014, and the power calculations are based on the most recent mortality rates. If the decreasing trends continue (with further advances in treatment outcomes), the observed death rates could be lower by up to a quarter relative to those used in the power calculations. Assuming 469 prostate cancer deaths from prostate cancer at 15 years, instead of 581, would reduce the statistical power and allow us to detect a minimal difference of 31% (HR ≤ 0.69).

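### Does the mortality test fail to control error because the plan does not say whether 10 or 15 years is the deciding horizon, or what alpha remains after the interim looks?

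*Combined protocol and SAP*

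**What the plan says.** Section 6 sets the endpoint without a date: "The main outcome of the trial is prostate cancer mortality", analysed by intention to screen with Cox regression. It adds "Follow-up starts at randomisation, and ends at death", with no common closing date. Two detectable effects follow. The first reads "the expected number of prostate cancer deaths in the control arm is 222 at 10 years, with sufficient statistical power", at 80% power and two-sided alpha 0.05, for a hazard ratio of 0.67. The second reads "At 15 years of follow-up, the expected number of deaths in the control arm is 451, with a minimal detectable effect size of 26" per cent, a hazard ratio of 0.74, with no separate alpha.

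Section 7 allows early stopping for benefit or harm. It says that interim analyses "are performed at five and eight years in accordance with sequential analysis rules (total alpha spending 0.005 of the two interim analyses", following O'Brien-Fleming.

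Two other places bear on the horizon. In section 5, "Table 1. Planned schedule of the trial conduct" ends at years 9-10. In section 8, the calculation for falling mortality is made at 15 years: "Assuming 469 prostate cancer deaths from prostate cancer at 15 years, instead of 581, would reduce the statistical power and allow us to detect" a 31% difference. Neither place calls its horizon the main analysis.

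**The concern.** A sequential design needs a final analysis and a level for it. This plan gives interim looks and an interim alpha total, then two candidate end points and no label on either. Read strictly, the team could see the 10-year result and only then decide whether it was the final test or an early report on the way to 15 years.

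That freedom would matter most if the true effect is modest. Section 8 takes the 20% reduction in the European trial and says that if the kallikrein panel and MRI "both have 90% sensitivity for clinically relevant prostate cancer, a realistic effect size might be" a 16% reduction. At 16-20% a non-significant 10-year result is more likely than a significant one, so readers would want to know what it meant. There is also a plain error-rate worry: testing at full 0.05 at both horizons, on top of the interim looks, would exceed 5%.

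**Working it through.** **Inputs.** Control deaths C = 222 (10 years) and 451 (15 years), hazard ratios 0.67 and 0.74, two-sided alpha 0.05 and 80% power (section 6). Allocation 1:3, so 16,750 screened and 50,250 control (section 3). Interim total 0.005 at years 5 and 8 (section 7).

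**1. The plan's own figures.** Control rates agree: 222/50,250 = 44.2 and 451/50,250 = 89.8 per 10,000, against 44 and 90 stated. Total deaths are D = C(1 + HR/3), giving 271.6 and 562.2. Two standard formulas were used:

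- Schoenfeld: power = Φ(|ln HR| × √(D × 0.25 × 0.75) − 1.96)
- Wald: power = Φ(|ln HR| / √(1/C + 3/(C × HR)) − 1.96)

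| Horizon | HR | Power, Schoenfeld | Power, Wald | Detectable at 80%, Schoenfeld | Detectable at 80%, Wald |
|---|---|---|---|---|---|
| 10 years | 0.67 | 81.5% | 72.2% | 32.5% | 36.2% |
| 15 years | 0.74 | 87.1% | 81.2% | 23.8% | 25.6% |

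The stated 33% matches Schoenfeld and the stated 26% matches Wald. Each can be reproduced, though not both by one of these formulas.

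**2. Interim bounds.** Deaths at years 5 and 8 are not in the documents, so three accrual curves were assumed: a power-law and an exponential cumulative hazard, both through 222 and 451, and a straight line to 10 years. They give 66, 84 or 111 control deaths at year 5 and 150, 158 or 178 at year 8. The correlation between two looks is the square root of the ratio of deaths. O'Brien-Fleming-shaped bounds have |Z| at year 5 equal to k√(d8/d5) and |Z| at year 8 equal to k, with k chosen so that the total crossing probability is 0.005. This gives about 4.2, 3.9 or 3.6 at year 5 and 2.8 at year 8. The bounds do not depend on the final horizon.

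**3. Type I error with a single final test.**

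| Final horizon | Error if the final test uses an unreduced 0.05 | Final nominal p that holds 5.0% overall |
|---|---|---|
| 10 years | 0.0508 / 0.0506 / 0.0503 | 0.0492 / 0.0493 / 0.0497 |
| 15 years | 0.0529 / 0.0528 / 0.0526 | 0.0470 / 0.0471 / 0.0474 |

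Using 0.0492 leaves the 10-year detectable effect at 32.5% (Schoenfeld), or moves it from 36.2% to 36.3% (Wald). Using 0.0470 moves the 15-year effect from 23.8% to 24.0%, or from 25.6% to 25.9%.

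**4. Both horizons as decision tests at 0.05.** The correlation is √(222/451) = 0.702. The chance of at least one false rejection is 0.083, or 0.084 with the interim looks included.

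**5. Power at the effects discussed in section 8**, at p < 0.0492 (10 years) and p < 0.0470 (15 years), ignoring early stopping:

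| True reduction | 10 years, Schoenfeld / Wald | 15 years, Schoenfeld / Wald |
|---|---|---|
| 16% (HR 0.84) | 24% / 23% | 43% / 40% |
| 20% (HR 0.80) | 36% / 33% | 63% / 57% |

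**6. Does the 0.005 identify the horizon?** The O'Brien-Fleming-type spending function 2(1 − Φ(1.96/√t)) would have spent 0.017-0.028 by year 8 for a 10-year final analysis and 0.0007-0.0018 for a 15-year one. The stated 0.005 lies between these ranges. A fixed 0.005 can be used with either horizon.

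**The case for a change.** The strongest case for acting is that the horizon cannot be proved from the text and that it matters. Several features lean to 10 years: alpha and power are written only there, looks at 5 and 8 years suit it, and the schedule stops at years 9-10. But that schedule lists recruitment and screening rounds, not analyses, and section 8 tests robustness at 15 years only. Moving from 10 to 15 years nearly doubles power for a 16-20% reduction, and settling the matter in writing would cost very little.

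Much of this stands: the horizon is unnamed and inference does not fully settle it. Three things keep it from becoming a defect.

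- The harmful version, two full-alpha tests, appears nowhere in the plan. Stated sequential rules and a stated interim alpha point to ordinary error control.
- The power contrast depends on the true effect being 16-20%. At the design hazard ratio of 0.67, 10-year power with p < 0.0492 is 81% (Schoenfeld) or 72% (Wald), so significance is the likelier result. Section 8 also expects the shorter interval for men with PSA above 3 to offset the loss at least partly. Low power at small effects is a separate question.
- Committing to one horizon is not clearly better. It would give up a confirmatory claim at the other, whereas a spending rule could serve both. As an illustration only, spending 0.02 cumulatively through year 10 gives nominal levels of about 0.018-0.019 at 10 years and 0.038 at 15 years. That holds 5% overall and raises the 15-year detectable effect by about one percentage point. The choice is a trade-off for the sponsor, and the statistics do not force one answer.

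**Conclusion.** No change is called for. The plan leaves unwritten a detail that analysts would fill sensibly: one deciding mortality analysis, with the 0.005 inside an overall two-sided 0.05. On that reading the error is 5.0%. Ignoring the deduction altogether takes it to 5.3% at most, and making the deduction costs about 0.2 percentage points of detectable effect at most. The final nominal level (about 0.049 at 10 years, 0.047 at 15) depends on the deaths seen at each look, so its absence from the plan is a reporting detail.

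The 8.3-8.4% figure belongs to a rule the plan does not contain and should carry no weight. The unnamed horizon is the more substantial part. It affects when a claim can be made and with what power, but naming one would not change the validity of the test or the power at either horizon.

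These figures rest on the assumed death curves for years 5 and 8, information proportional to deaths, and 0.05 in section 6 being the overall alpha. The three curves tried change the type I error by no more than 0.0005.

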### 3. TARGET POPULATION

We will identify all 67,000 men aged 50-63 years and residing in Tampere or Helsinki from the Population registry, and after exclusion of men with a prior diagnosis of prostate cancer (expected number 200), randomize them into two trial arms in ratio 1:3 (16,750 men allocated to the screening arm expected). Randomization is based on computer-generated random numbers and will be conducted in five batches annually (10% of the entire population at a time). This procedure is chosen in order to include only men alive and free of prostate cancer (with up-to-date information on cancer and vital status). Men with a permanent address abroad are not eligible.

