### 4. METHODS

#### Study rationale

Frequent adverse effects have so far tipped the balance of benefits and harms against prostate cancer screening, and therefore we will focus on employing the best possible means for reducing them. The project proposal introduces a novel concept for PC screening that minimises overdiagnosis and overtreatment, while retaining the mortality benefit to shift the balance of screening benefits and harms to a favourable net effect. The strategy for implementation as a randomised screening trial utilises three levels of risk assessment (PSA, kallikrein panel and MRI) before the diagnostic procedure (prostate biopsy), each aimed at eliminating detection of indolent disease. The study hypothesis is that by virtue of the novel

three-tiered screening algorithm, the beneficial screening effect (prostate cancer mortality reduction) can be retained, while the overdiagnosis can be largely eliminated. The impact of our integrative approach has never been evaluated – each of the methods has only been assessed in isolation. The breakthrough potential of the proposal lies in combining the three novel approaches and taking them to the forefront of applied research through a randomised trial. The key impact of the study is in defining whether the overall balance of benefits and harms of prostate cancer screening can be reversed by applying the best possible methods to detect only clinically important disease. If the study hypothesis is affirmed, it opens the way to introduction of prostate cancer screening. If the balance of harms and benefits is still unfavourable, the problem of overdiagnosis in prostate cancer may be intractable.

The main adverse effect of screening, i.e. overdiagnosis has to be minimised. The best potential methods for avoiding it are: a kallikrein panel, multiparametric MRI and flexible screening interval. Each of the methods has been shown to reduce the detection of Gleason<7 prostate cancer by at least a third, while missing only 10-15% of the more aggressive cases. Their combined effect has not, however, been studied, nor have they been evaluated in a randomised screening trial, only non-randomised evaluation of each method separately has been reported.

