#### Screening protocol

Briefly, we will first screen men with total PSA and then use an array of four biochemical markers (4Kscore) among men with PSA>3 ng/ml to improve the diagnostic accuracy for clinically significant cancer (Gleason≥7), while reducing the number of biopsies and detection of Gleason<7 cancers. For diagnostic assessment of screen-positive men, we will use multiparametric MRI, aimed at reducing the detection of Gleason<7 prostate cancer by at least 50% by the combination of the screening test and diagnostics (Figure 1). Finally, the baseline serum PSA is used for determining the optimal screening interval, ranging 2-6 years.

[figure not shown]

Figure 1. Using three layers of risk stratification to identify men at highest risk.

The control arm will receive usual care, with no intervention (apart from collection of registry data for all men in both arms on the outcomes, including PSA testing, prostate cancer incidence and mortality, as well as questionnaire surveys for some subgroups).

Men in the screening arm will be invited to the first screen over a two-year period. We expect similar participation as in the previous Finnish prostate cancer screening trial (two thirds or 11,167 participants). This would mean that we would screen roughly 560 men per month (assuming 10 months of effective screening annually) (Figure 2).

In the baseline survey at entry to the study, screening participants are asked about their family history of prostate cancer, as well as established or suspected risk factors for prostate cancer (including BMI, alcohol consumption, physical activity and consumption of some foodstuffs). Information will be also collected on previous PSA tests and possible prior prostate biopsy from the hospital databases.

A 30 ml blood sample will be drawn at one of the service sites of the regional laboratory networks (HUSLab and FimLab) to an EDTA tube, with plasma and serum separated and frozen. Total and free PSA are analysed at HUSLab and FimLab with electrochemiluminescence immunoassay (ECLIA) for COBAS® 6000 analyser (Roche Diagnostics, Rotkreuz, Switzerland). Calibration is performed using the WHO standards (WHO 96/670 and 68/668 for total and free PSA).

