## 7. ETHICAL ISSUES

Screening is by definition targeting people free of the target condition, and the benefit per participant is nearly always small. Consequently, any risk must also be small to justify the intervention. The primary screening tests are based on biochemical analyses of a blood sample, with minimal risks. All the other procedures in the trial (diagnosis and treatment among screen-positive men) are conducted in accordance with the normal standards of care and pose therefore no ethical issues. The study protocol will be submitted for review by the ethical committees of the Uusimaa and Pirkanmaa hospital districts. Permission for cancer registry linkage will be obtained from the National Institute for Health and Welfare (THL). Written informed consent is obtained from all screening participants for both the intervention and collection of data from electronic health records and health care registers for the analyses of the trial (cancer registry, cause of death registry, hospital discharge registry, regional laboratory and national prescription databases). Information about screening covers probabilities of abnormal screening test result, prostate cancer detection at biopsy given screen-positive result, frequency of biopsy complications, treatment options with their adverse effects, overdiagnosis in screening, as well as mortality impact of screening. The information is provided as a decision aid with graphically presented numerical results, modified from the earlier Finnish screening trial. A trial website will also be constructed to provide information on the progress of the study for the participants. According to the Finnish regulation, no consent is required for non-compliers or men in the control arm, but register data can be collected with permission from THL after an ethics committee review.

The trial can be stopped early for benefit or harm, if evidence for difference between the arms is obtained. For assessment of harm from the intervention, biopsy and treatment complications will be analysed, as well as incidence of advanced cancer (as an indicator of cancers missed by screening) and Gleason <7 cancer (as indicator of overdiagnosis) by arm are performed annually for the data monitoring committee. Monitoring of the main end-point (prostate cancer mortality) is carried out by an external committee. Interim analyses

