Active surveillance, with curative treatment postponed until signs of disease progression, has gained popularity in management of prostate cancer recently (Moschini 2017). Though treatment results of active surveillance have been highly favourable, it has a potential to decrease the screening impact as in some cases it may result in undertreatment and poor outcomes.

Statistical power can also be reduced by dilution of the contrast in the intervention between the arms. Spillover means intervention becoming available also to the control arm during the trial. PSA testing prior to baseline would also reduce the expected impact of screening. PSA testing frequency (including diagnostic assessment of men with urological complaints, as well as monitoring of men treated for prostate cancer, besides testing for screening purposes) was very high (up to >20%) in Finland after 2000 (Kilpeläinen 2017), but the stark reduction in prostate cancer incidence by a quarter in the past 10 years clearly suggest a decline its popularity.

Any future changes on clinical practice regarding diagnosis or management of prostate cancer will be incorporated in the protocol and applied to all men in the study. For instance, a faster, simpler MRI protocol (biparametric imaging) is being developed, and recent evidence indicates that adding abiraterone in the first-line endocrine treatment of metastatic prostate cancer may improve treatment results.

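### Mortality, but not the Gleason<7 overdiagnosis measure, gets a secondary analysis for non-attendance and outside PSA testing, so a small by-arm excess would not alone show that overdiagnosis was removed

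*Combined protocol and SAP*

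**What the plan says.** Section 6 bases the main mortality analysis on the randomised arms: "An intention to screen analysis will be performed, with all men in the groups defined by random allocation, regardless of compliance". It then adds one adjusted analysis, for mortality: "A secondary analysis of prostate cancer mortality will be performed using the Cuzick method to correct for non-compliance and contamination". The overdiagnosis measure appears among the intermediate outcomes as "cumulative incidence of low-risk cancer (Gleason<7) as an indicator of overdiagnosis", with no adjustment, sensitivity analysis or estimand attached. Section 7 has the same outcome compared between arms each year, also unadjusted: "Gleason <7 cancer (as indicator of overdiagnosis) by arm are performed annually for the data monitoring committee".

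Three other places bear on it:

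- Study rationale (section 4) makes it part of the hypothesis that "the overdiagnosis can be largely eliminated".
- Section 8 discusses spillover to controls and PSA testing before baseline, but only as lowering power and the expected impact of screening. It reports that PSA testing frequency "was very high (up to >20%) in Finland after 2000". That figure includes diagnostic and monitoring tests, and testing is said to have declined since.
- Screening protocol (section 4) says registry data on PSA testing are collected for all men in both arms.

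**The concern.** Non-attendance and outside testing pull both contrasts towards no difference. For mortality that works against the trial's hypothesis. For Gleason<7 it works in favour, because the hypothesis is that little excess exists. The plan's Background explains the null mortality result of the U.S. trial partly by contamination, and the same reasoning would apply to a null Gleason<7 contrast. The Background also attributes much of current prostate cancer incidence to PSA testing, so usual care is not free of overdiagnosis. A small excess over usual care could mean that the pathway adds little overdiagnosis, or that both arms overdiagnose. Nothing pre-specified separates the two.

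Study rationale says that a confirmed hypothesis would open the way to introducing screening, so how this contrast is read matters to the trial's conclusion.

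**Working it through.** **1. The plan's first-round count reproduces.** 67,000/4 = 16,750 invited (50,250 controls); × 2/3 = 11,167 attenders; × 0.13 = 1,452 with raised PSA; × 0.60 = 871 referred to MRI; × 0.60 = 523 MRI-positive (plan 521); × 0.55 = 287 cancers (plan 290, and 290/11,167 = 2.6%). The plan words the 55% as a share of men referred to MRI, which would give 871 × 0.55 = 479, so it fits only MRI-positive men. I use 290.

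**2. Gleason<7 yield.** Diagnostic procedures expects 75–80% of these cases to be Gleason 7 or higher, so 20–25% are Gleason<7.

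- Cases: 290 × 0.20 = 58; 290 × 0.25 = 72.5.
- Per 10,000 invited: 58/16,750 = 34.6; 72.5/16,750 = 43.3.
- Per 10,000 attenders: 58/11,167 = 51.9; 72.5/11,167 = 64.9.

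**3. Non-attendance alone.** If invitation does not change incidence in non-attenders, by-arm excess = a × excess among attenders, with a = 11,167/16,750 = 0.667. The per-attender excess is therefore 1/0.667 = 1.5 times the by-arm excess.

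**4. Adding outside testing.** Let rs be the Gleason<7 risk per attender, c the share of controls and of non-attenders tested once outside the trial, m the Gleason<7 yield per such man relative to rs, and r0 the risk in untested men, with f = r0/rs.

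- Control arm: C = c·m·rs + (1 − c)·r0
- Screening arm: a·rs + (1 − a)·C
- Excess: a·(rs − C), which is a·rs·(1 − c·m) when r0 = 0
- Excess is zero at c* = (1 − f)/(m − f)

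The documents do not give m. Three values can be built from their figures:

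- m = 2, from the design aim for the combined algorithm, "aimed at reducing the detection of Gleason<7 prostate cancer by at least 50" per cent.
- m = 1.12–1.20, if outside work-up includes MRI: 2 × (1 − 0.44) to 2 × (1 − 0.40), from the Background's 40–44% lower low-risk detection.
- m = 3.4, if the three methods each cut detection by a third and act independently: 1/(2/3)³ = 3.375.

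| m | Excess per 10,000 invited at c = 20%, f = 0 | c* at f = 0 | c* at f = 0.2 |
|---|---|---|---|
| 1.12–1.20 | 26–34 | 83–89% | 80–87% |
| 2 | 21–26 | 50% | 44% |
| 3.4 | 11–14 | 30% | 25% |

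For m = 2: 34.6 × (1 − 0.4) = 20.8 and 43.3 × 0.6 = 26.0. That is 0.667 × 0.6 = 40% of the per-attender excess.

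**5. Would the excess still be seen?** Take the midpoint rs = 290 × 0.225/11,167 = 58 per 10,000, c = 20%, and a two-sided 5% comparison of 16,750 with 50,250 men.

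- m = 2: 46.7 vs 23.4 per 10,000 at f = 0 (ratio 2.0, power 0.99); 49.9 vs 32.7 at f = 0.2 (ratio 1.5, power 0.86).
- m = 3.4: 52.1 vs 39.4 (ratio 1.3, power 0.58); 55.2 vs 48.8 (ratio 1.1, power 0.18).

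**6. What is c?** The figure in section 8 has no time unit. If it were annual and independent from year to year, 20% would become 1 − 0.8⁵ = 67% over five years; 5% a year would become 1 − 0.95⁵ = 23%. Independence overstates the share where the same men are retested, and the figure includes monitoring of treated men. The documents therefore do not place c above or below c*.

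**The case against.** **Intention to screen is the right policy contrast, and it is like for like.** This stands. Main mortality and Gleason<7 are both unadjusted, per man invited and against usual care. A reader might infer that the plan reports benefit per attender and harm per man invited. The documents do not say so: the adjusted mortality analysis is secondary, and the mismatch arises only if that result is set beside the unadjusted Gleason<7 result.

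**Outside testing need not hide the excess.** This also stands. A reader might infer that a PSA-tested control arm would make overdiagnosis look eliminated. Adding outside tests to controls only, with m = 2, would put the zero point at a/m = 0.667/2 = 33%. But that treats the third of the screening arm who do not attend as never tested, although they live under the same usual care. Tested like controls, the zero point is 44–50%.

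**A relative yield of 2 may be too high.** The Background calls MRI a new standard, and Study rationale describes uniform diagnostics for both arms in the same centres. The 50% is a design aim, and its comparator is not stated. This is fair, and it keeps m open.

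**Other features push the other way.** Systematic biopsy of a random sample of test-negative men and of MRI-negative men with high PSA density, and the repeat rounds, all raise Gleason<7 incidence in the screening arm. The working above covers one round only.

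None of this supplies the missing analysis. An increment over usual care and the elimination of overdiagnosis are different quantities, and the plan has an estimate only of the first.

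**Conclusion.** The gap is real and moderate. Section 6 plans a secondary adjustment for mortality and none for the overdiagnosis indicator, whose contrast is shrunk in the direction of the hypothesis. Non-attendance alone hides a third of the per-attender excess, on the plan's own participation figure. With 20% outside testing and m = 2, about 40% of it remains visible (37% at f = 0.2), and that would still be detectable.

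The documents do not support the claim that the excess would disappear. That needs about 44–50% tested at m = 2, 83–89% if work-up includes MRI (with no cases in untested men), or 25–30% at m = 3.4. These figures assume one round of outside testing, non-attenders tested like controls, and first-round yields. Both c and m are assumptions. The by-arm analysis itself is valid and should stay.

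**What to change.** In section 6:

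1. Keep the by-arm Gleason<7 analysis and state that its estimand is the increment over usual care.
2. Add a secondary Gleason<7 analysis adjusted for non-attendance on the same basis as mortality, so that benefit and harm are each given per man invited and per attender.
3. Report control-arm PSA testing from the registry data beside every Gleason<7 result, including the annual comparison in section 7.
4. Add a contamination sensitivity analysis that gives outside PSA testing its own Gleason<7 yield, over a stated range. A plain Cuzick correction would treat outside testing as the same intervention as the trial pathway.
5. State in advance that a by-arm ratio near 1 will not be read as overdiagnosis eliminated unless analyses 2 and 4 agree.

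A by-arm comparison in men with no PSA test before randomisation is optional. It would remain a randomised comparison, but it deals with prior testing only, not with testing during the trial. It also needs prior-test data for both arms, whereas Screening protocol clearly describes those data only for screening participants.

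The cost is SAP wording and a little more analysis of PSA-testing data already planned for both arms. The adjusted estimates will have wider intervals and will depend on the assumptions made.
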